
utilization in participants with COPD and an eosinophilic phenotype experiencing an acute COPD exacerbation.
	
• Time to ready-for-discharge in hospitalized participants based on clinical assessment.• Time to ready-for-discharge in hospitalized participants based on VBG results• Total number of COPD-related hospital-stay hours during the first 28 days after discharge from the index acute COPD exacerbation (may include more than 1 COPD-related admission to the hospital).• Total number of COPD-related hospital-stay hours during the 8-week trial period (may include more than 1 COPD-related admission to the hospital).• For hospitalized participants: Hospital readmission rate during the first 28 days after discharge from the index acute COPD exacerbation and during the 8-week trial period.• Total number of all-cause hospital-stay hours during the first 28 days after discharge from the index acute COPD exacerbation (may include more than 1 admission to the hospital).• Total number of all-cause hospital-stay hours during the 8-week trial period (may include more than 1 admission to the hospital).• Incidence and rate of unscheduled visits for urgent care primarily related to COPD symptoms.• Incidence and rate of unscheduled calls for urgent care primarily related to COPD symptoms.• ICU admission rate during the first 4-week trial period.• Invasive ventilation rate during the first 4-week trial period.
---	---

 To explore the effect of rademikibart compared with placebo as an adjunct to standard therapy on improvement in symptoms, usage of rescue medications, and health-related quality of life/PROs in participants with COPD and an eosinophilic phenotype experiencing an acute COPD exacerbation. 	
 CFB in Dyspnea NRS at scheduled timepoints. Total dose/use of systemic corticosteroids. Use of daily puffs of rescue medication. CFB in SGRQ total score compared to placebo at Weeks 4 and 8. Proportion of participants with SGRQ improvement ≥ 4 points at Week 4 and Week 8. CFB in CAT total score compared to placebo at Week 1, Week 4, and Week 8. Proportion of participants with a decrease from Baseline in CAT total score ≥ 2 at Week 1, Week 4, and Week 8. CFB in clinical respiratory symptoms of COPD using the Evaluating Respiratory Symptoms in COPD (E-RS: COPD) comprised in the EXACT-PRO tool during the Follow-up Period at Week 8.
---	---

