6.3. Treatment Assignment

Participants will be randomized in a 1:1 ratio to 1 of the following double-blinded treatment groups, stratified by severity of the acute COPD exacerbation (requiring hospitalization or not [yes/no]) at baseline, and baseline smoking status [current or former]:

- **Rademikibart** 600 mg dose administered as 4 SC injections of 1 mL (150 mg) each.
- **Matching Placebo** administered as 4 SC injections of 1 mL each.

IP (rademikibart 600 mg SC or placebo SC) will be administered on Day 0 as per the SoA (Table 5).

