8. Participants with a history of clinically significant renal, hepatic, cardiovascular, metabolic, neurologic, hematologic, ophthalmologic, respiratory, gastrointestinal, cerebrovascular, substance and/or alcohol abuse, or other significant medical illness or disorder which, in the Investigator's judgement, could interfere with the trial or require treatment that might interfere with the trial. Specific examples include but are not limited to poorly controlled diabetes.
9. Another clinically significant pulmonary or systemic disease associated with an elevated peripheral blood eosinophil count (eg, allergic bronchopulmonary aspergillosis, eosinophilic granulomatosis with polyangiitis, hyper-eosinophilic syndrome, and helminth infection).
10. Known or suspected history of immunosuppression, including history of invasive opportunistic infections (eg, tuberculosis, histoplasmosis, listeriosis, coccidioidomycosis, pneumocystosis, aspergillosis), despite infection resolution; or unusually frequent, recurrent or prolonged infections, in the opinion of the Investigator.
11. History of known immunodeficiency disorder (including human immunodeficiency virus [HIV]-1 or HIV-2).
12. Known medical history of hepatitis B or C.
13. History of alcohol abuse and/or drug abuse within 12 months prior to Screening Visit 1a and/or 1b.
14. History of cancer except basal cell carcinoma or in situ carcinoma of the cervix treated with apparent success with curative therapy >1 year prior to entry or other malignancies treated with apparent success with curative therapy >5 years prior to entry.
15. Having undergone lung volume reduction surgery or lung resection for any other reason, eg, lung carcinoma.
16. Chronic treatment with long-term oxygen therapy (LTOT) or nocturnal oxygen therapy required for >15 hours a day. Oxygen pro re nata (PRN) use (ie, ≤15 hours per day) is not exclusionary. Oxygen use during an exacerbation is permitted.
17. Participants on long-term macrolide (eg, azithromycin) therapy, unless on stable therapy for >12 months, with the exception of prior treatment for an acute COPD exacerbation.

Additional Exclusion Criteria for Current Acute COPD Exacerbation:

18. Fever recorded as >38°C and/or a suspected pulmonary infection (chest radiograph demonstrating consolidation).
19. Any condition (ie, respiratory failure necessitating non-invasive or invasive ventilation, or impending hemodynamic compromise, or impending intensive care unit [ICU]

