8.2.2. Permitted Concomitant Therapy

8.2.2.1. COPD Medications and Non-Drug Therapies

To be eligible to be randomized in this trial, participants must present with an acute COPD exacerbation characterized by an eosinophilic phenotype and required systemic corticosteroids as SoC treatment in the urgent healthcare setting for the acute exacerbation. SoC for the index acute exacerbation is defined for this protocol as treatment with oral/systemic corticosteroid[s] (40 mg/day prednisone or equivalent) for 5 days with or without antibiotic(s) for 7 days; the modification of the dose and/or duration of prednisone (40 mg/day or equivalent) and/or the antibiotic is not recommended but may be allowed according to the Investigator's/medically qualified designee's judgement.

The start of SoC is defined as the start of either oral or systemic corticosteroids(s) or antibiotic(s), whichever is earliest.

Note: SoC must be documented in the participant's source documentation and in the eCRF. The use of other medications for treatment of the index acute COPD exacerbation and any subsequent COPD exacerbation(s), if applicable, is at the discretion of the Investigator or medically qualified health care personnel. Use of medication for treatment of subsequent exacerbations does not need to follow the SoC requirements for the index acute exacerbation.

In addition, participants are instructed to continue their regular COPD maintenance treatments (eg, LAMAs, LABA/ICS combinations, LABA/LAMA combinations, or LABA/LAMA/ICS combinations) for the duration of the trial. However, participants must withhold the morning dose of usual scheduled COPD medications on the morning of the spirometry assessments, except when treatment is needed for an acute COPD exacerbation.

Note: Modification(s) of the dosing regimen for the regular COPD maintenance treatments is(are) permitted as deemed medically appropriate by the Investigator/medically qualified designee; the modifications will be recorded in source documents and eCRF.

Other concomitant COPD maintenance medications may be allowed at the discretion of the Investigator following consultation with the Sponsor Medical Monitor, with the exception of short-acting anticholinergics for use as rescue medication.

Oxygen for intermittent use or PRN therapy ≤ 15 hours per day is allowed. LTOT or nocturnal oxygen therapy required for >15 hours is excluded throughout the trial.

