10.1. Treatment Failure

Treatment failure is defined as death due to any cause, (re)admission to a hospital for COPD, ED (re)visit or unscheduled medical visit for worsening of COPD symptoms, or the necessity to intensify pharmacologic treatment (including second course of systemic steroids for COPD exacerbation) within 28 days after randomization.

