13.2. Sample Size Determination

Approximately 160 participants with COPD exacerbation will be randomized using 1:1 allocation ratio to rademikibart 600 mg SC or placebo. The sample size calculation is based on the statistical analysis of the primary endpoint of treatment failure rate.

To account for a 5% dropout rate, approximately 160 participants will be randomized to ensure that 152 participants are evaluable. Assuming treatment failure rates of 22.5% for the rademikibart group and 45% for the placebo group up to 28 days after randomization, this sample size will provide at least 80% power to detect a difference at a 2-sided Type I error rate of 5%. Conditional power will be calculated during the IA and the final sample size will be determined according to the prespecified rules.

To ensure that the sample size is reasonably sufficient, an unblinded sample size re-estimation will be conducted when approximately the first 80 participants in total have had the opportunity to complete the trial or discontinue early (ie, no ongoing participants will be included in this sample size re-estimation procedure). The unblinded sample size re-estimation procedure for this trial will not allow for a reduction in the planned sample size or an increase in sample size greater than 40 participants per group (80 participants total). This sample size re-estimation procedure will be conducted by a statistician who is not associated with the conduct or final analysis of the trial. No penalty will be applied to the p-values or confidence intervals for assessing treatment difference from placebo due to this sample size re-estimation procedure. The independent statistician and DMC will recommend to the Sponsor any changes required to the sample size. Results from the IA will be communicated to a limited number of the Sponsor's senior management team who are independent of the clinical trial team and will be identified in the unblinding plan before the IA is performed.

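### For index inpatients, the treatment-failure rule does not count new ventilation or ICU transfer unless death, a drug step-up or a later qualifying event also occurs

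*Protocol*

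**What the plan says.** Section 10.1, repeated in the synopsis, lists the routes to treatment failure. Those other than drug treatment are "death due to any cause, (re)admission to a hospital for COPD, ED (re)visit or unscheduled medical visit for worsening of COPD symptoms". The remaining route concerns drugs only: "or the necessity to intensify pharmacologic treatment (including second course of systemic steroids for COPD exacerbation) within 28 days after randomization". Neither place mentions ventilation, ICU transfer or any other change in level of care.

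Hospitalized participants are a planned part of the primary population. Section 6.3 has randomization "stratified by severity of the acute COPD exacerbation (requiring hospitalization or not [yes/no]) at baseline" and by smoking status. Section 13.4.5 tests a common risk difference across those strata.

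Elsewhere the protocol treats these events as serious:

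- Exclusion 19 (Section 7.2) names "respiratory failure necessitating non-invasive or invasive ventilation, or impending hemodynamic compromise, or impending intensive care unit [ICU" among the conditions that can bar entry when the Investigator judges that they would interfere with the evaluation.
- Section 8.2.2.2 does not allow enrolment of anyone who needs acute CPAP.
- Table 2 (Section 5) has "ICU admission rate during the first 4-week trial period" and "Invasive ventilation rate during the first 4-week trial period", but only as exploratory resource-use endpoints. Non-invasive ventilation has no endpoint.

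**The concern.** Admission, an ED visit and an unscheduled visit all presuppose that the participant is outside hospital. For someone still an inpatient for the index event, two routes remain: death and drug intensification. A surviving inpatient whose breathing fails after randomization, and who is supported by ventilation or ICU care without a drug step-up, meets neither.

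Section 4.3.3 says the endpoint is meant to show whether the drug reduces treatment failure for the index exacerbation, and Section 4.3.2 rests part of the rationale on effects within 24 hours of dosing. Early worsening in hospital is therefore within what the endpoint is supposed to measure. At stake is what the primary result means: the pooled risk difference combines a stratum in which such worsening counts with one in which it may not.

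**Working it through.** **Step 1. Apply the Section 10.1 rule to comparable courses.** These cases are constructed for illustration.

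| Course after randomization | Route met | Score |
|---|---|---|
| A. Index inpatient; Day 2 respiratory failure, ventilated in ICU, no drug step-up, survives, no later event by Day 28 | none | non-failure |
| B. Randomized as not hospitalized; same Day 2 worsening, admitted | admission for COPD | failure |
| C. Randomized as not hospitalized; one unscheduled visit for worse symptoms on Day 20, treatment unchanged | unscheduled visit | failure |
| D. As A, but a drug is stepped up, or the participant dies, or is readmitted or makes an ED or unscheduled visit for COPD by Day 28 | one or more | failure |

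The gap is course A only. Could an ICU transfer be read as a hospital admission? The rule says hospital, and Table 2 lists hospital readmission and ICU admission as separate endpoints, so that reading is weak.

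**Step 2. Check the drug-intensification fallback.** Section 8.2.2.1 says of the index regimen that "the modification of the dose and/or duration of prednisone (40 mg/day or equivalent) and/or the antibiotic is not recommended but may be allowed" at the Investigator's judgement. The protocol does not say whether such a change counts as intensification, so whether an inpatient is scored as A or D may depend on how a site reads the word.

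**Step 3. Reproduce the stated design.** Section 13.2: "Assuming treatment failure rates of 22.5% for the rademikibart group and 45% for the placebo group up to 28 days after randomization", two-sided 5%, 152 evaluable of 160 randomized, 1:1, hence n = 76 per arm.

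Dropout: 152 / 0.95 = 160.

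Power (normal approximation, pooled variance under the null):
z = [ |p2 − p1|·√n − 1.96·√(2·p̄·(1 − p̄)) ] / √(p1(1 − p1) + p2(1 − p2)), with p1 = 0.225, p2 = 0.45, p̄ = 0.3375.
z = (1.9615 − 1.3107) / 0.6495 = 1.002, so power = 84.2%.

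The unpooled version gives 85.5% and exact Fisher enumeration 80.0%. The claim of at least 80% power stands.

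**Step 4. Sensitivity to the gap.** The protocol gives neither the inpatient share nor any rate of in-hospital ventilation or ICU transfer. Assume that a share m of all placebo participants follow course A, with the rademikibart share either m/2 or m. As an illustration, half the participants inpatient and 4% of them following course A gives m = 0.5 × 0.04 = 2%. Two readings of the planning rates are possible:

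- Reading I: the 45% and 22.5% include these events and the rule misses them, so the shares are subtracted.
- Reading II: the rates are as the rule scores them, and the added clause would bring these events in, so the shares are added.

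| m (placebo) | Placebo participants per 76 | I, drug share m/2 | I, drug share m | II, drug share m/2 | II, drug share m |
|---|---|---|---|---|---|
| 1% | 0.8 | 82.9% | 84.7% | 85.4% | 83.7% |
| 2% | 1.5 | 81.6% | 85.3% | 86.6% | 83.2% |
| 3% | 2.3 | 80.2% | 86.0% | 87.7% | 82.7% |
| 5% | 3.8 | 77.3% | 87.3% | 89.7% | 81.9% |

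Example (I, m = 5%, drug share m/2): rates 40% and 20%; z = (1.7436 − 1.2702) / 0.6325 = 0.748; power 77.3%.

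Under I, omitting the events gives power between 77.3% and 87.3% against 84.2% as planned. Under II, counting them gives between 81.9% and 89.7%. The direction depends on assumptions that the protocol does not settle.

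**The case against.** The case for leaving the rule alone has several parts, and much of it stands.

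- A reader might infer that the endpoint cannot register any in-hospital collapse. The text does not support that. Death counts, any drug intensification counts (a second steroid course is only an example), and every other route reopens after discharge within 28 days. Many ventilated participants would also have drugs stepped up.
- A reader might infer that the trial is underpowered. It is not shown to be. Section 13.2 attaches its rates to the treatment-failure endpoint, which Section 10.1 defines without these events. A loss of power appears only if the rates were meant to include them and the drug also lowers their frequency. With equal shares in both arms, power rises.
- A reader might infer that an excess of respiratory failure on the drug would go unseen. It could be missing from the primary endpoint, but life-threatening events and prolonged hospitalization are SAEs (Section 11.3.2), the DMC reviews safety (Section 6.7), and ICU admission and invasive ventilation are exploratory endpoints.
- The arm comparison is fair. Randomization and the test are both stratified by hospitalization, so like is compared with like within each stratum.
- Exclusion 19 removes some of the participants most at risk, and its stated ground is interference with evaluation, so it does not by itself make later ventilation a treatment failure.
- Section 4.3.3 defends the endpoint as widely used in earlier exacerbation trials.

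None of this puts course A on the list. A statistical analysis plan, which was not available, could add data conventions, but the protocol itself defines the endpoint, in the same terms in two places.

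**Conclusion.** The point holds in a limited form. As written, the primary endpoint scores as non-failures those index inpatients who are newly ventilated or moved to ICU for COPD after randomization, survive, have no drug step-up and have no later qualifying event by Day 28. The same worsening in the non-hospitalized stratum is a failure.

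The number of such participants is unknown and probably small. At an assumed 1% to 5% of the placebo arm it is about 1 to 4 of 76. No stated sample size or power figure is wrong, the effect on power could go either way, and type I error is unaffected. The defect is in what the endpoint measures: it omits a serious non-fatal failure in one randomization stratum. This is an inexpensive improvement to the definition and does not invalidate the design.

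**What to change.** Add one scoring clause to Section 10.1 and the same clause to the synopsis:

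> *or, in participants hospitalized for the index exacerbation, new initiation of non-invasive or invasive ventilation, or transfer to ICU, for COPD after randomization and within 28 days*

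Date the failure at that event. The word *new* keeps out stable CPAP begun before Screening, which Section 8.2.2.2 permits. It would also help to state whether a change to the index steroid or antibiotic regimen under Section 8.2.2.1 counts as intensification for scoring. The clause changes scoring only and prescribes no treatment.

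Keep the current definition as a supplementary analysis of the primary endpoint.

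Cost: protocol wording. ICU admission is already collected (Section 10.6) and invasive ventilation is already an endpoint (Table 2); non-invasive ventilation may need one added eCRF field. The downside is that the primary definition departs from the current one, which the supplementary analysis covers.

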10.2. Acute Exacerbation

COPD exacerbation data will be collected through Trial Day 56. For the purpose of this trial, COPD exacerbation is defined by protocol as either:

- Clinically significant worsening of COPD symptoms, including increases in dyspnea, wheezing, cough, sputum volume, and/or increase in sputum purulence.
- Exacerbation severity is further defined as moderate if treatment with systemic corticosteroids and/or antibiotics was required, or severe if they resulted in hospitalization or observation for over 24 hours in an ED or urgent healthcare facility.

All other exacerbations will be classified as “mild.”

For both moderate and severe events to be counted as separate events, they must be separated by at least 14 days.

The following information will be collected for each COPD exacerbation:

- Date of onset.
- Date of visit to healthcare provider or ED.
- Treatment.
- Resolution date.

10.3. Spirometry

Spirometry will be performed according to American Thoracic Society (ATS)/European Respiratory Society (ERS) guidelines (Miller et al. 2005; Graham et al. 2019) at the timepoints specified in the SoA (Table 5). Spirometry assessments, including FEV₁, and FVC (both the absolute measurement and the percentage of predicted normal value will be recorded), should be made as close to the scheduled timepoints as possible. In addition, protocol-specified clinic spirometry must be completed in accordance with the lifestyle restrictions as defined in Section 7.3.

Spirometry will be performed preferably in the morning; afternoon is allowable in the exceptional circumstance when morning spirometry cannot be performed. Current smokers need to be reminded not to smoke for at least 1 hour before spirometry. For each participant, the same spirometer and standard spirometric techniques, including calibration, will be used to perform spirometry at all visits and, whenever possible, the same person should perform the measurements.

Baseline FEV₁ is defined as the post-BD FEV₁ performed at Visit 2 before IP administration. If Visit 1b and Day 0 (Visit 2) are the same day, then post-BD spirometry does not need to be repeated.

At the timepoints SoA (Table 5), if the participant's condition allows, post-BD FEV₁ will be conducted approximately 15 to 30 minutes after the participant-administers 4 inhalations of albuterol (salbutamol) via MDI (ie, total of 400 mcg) using a spacer device.

It is anticipated that participants who are randomized into the trial will receive albuterol (salbutamol) as part of the routine treatment of the acute COPD exacerbation during Visit 2. In this case, spirometry should be scheduled to coincide with this treatment to allow post-BD recordings to be measured.

For hospitalized participants, post-BD spirometry should also be performed at the timepoints specified in the SoA (Table 5), including V3 and V4, provided the participant's condition allows.

Hospitalized participants discharged from the hospital prior to Visit 3 and Visit 4, or participants that were not hospitalized for the index COPD exacerbation, should return to the trial site or have a home health care visit for spirometry assessments at Visit 3 and Visit 4 when feasible.

If the participant can tolerate BD washout, at Visit 6, Visit 8, Visit 9, and on the day of discharge (only for hospitalized participants), spirometry will be performed prior to administering maintenance COPD medication(s) (pre-BD) and post-BD (as defined above). Participants should withhold their usual maintenance therapies on the day(s) when pre-BD spirometry is being performed as below:

- Withholding the last dose of salbutamol/albuterol or levosalbutamol/levalbuterol for at least 6 hours,
- Withholding the last dose of LABA for at least 12 hours [ultra-long-acting LABA like vilanterol should be withheld for at least 24 hours]
- Withholding the last dose of ipratropium bromide for at least 8 hours
- Withholding the last dose of LAMA for at least 24 hours

This washout period will be verified before performing the measurements. After completing the pre-BD spirometry, the post-BD spirometry should follow the steps as that at Visit 2 before IP administration.

Where multiple assessments are scheduled at the same time point, the sequence of assessments should ideally be as shown below. However, during the Screening Visit (Visit 1b) and/or the Randomization Visit (Visit 2), this order may be modified as needed, including instances where some or all of these procedures are performed as part of routine/urgent/ inpatient hospitalized care.

- PROs and other questionnaires.
- Vital signs.
- 12-lead ECG.
- FeNO.
- Spirometry assessment (pre-bronchodilator).
- Post-bronchodilator spirometry.
- e-diary download.
- Blood sampling and laboratory assessments.
- IP administration (only applicable to Visit 2).

Further details on spirometry will be available in a separate operational manual provided to the sites.

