13.4.6. Secondary Efficacy Endpoints

The rate of moderate and severe COPD exacerbations in the 28 days after randomization will be analyzed using a negative binomial regression model adjusting for randomization stratification factors and baseline characteristics. Full details of the model will be documented in the SAP.

The time to the first moderate or severe COPD exacerbation will be analyzed using a stratified log-rank test, adjusting for the randomization stratification factors. A Kaplan-Meier plot of the time to first moderate or severe COPD exacerbation will be provided.

A mixed model repeated measures analysis will be used to compare treatment groups with respect to the mean CFB in E-RS: COPD through Week 1, Week 2, and Week 4; and with respect to the absolute CFB in post-BD FEV₁ at Day 3, Week 1, and Week 4. The mixed model repeated measures model will include fixed factors for scheduled visit, treatment, the visit by treatment interaction, and will include covariates for the stratification factors and the respective baseline value of the continuous outcome. An unstructured covariance matrix will be used to model the within-participant covariance structure.

The FAS will be used for the secondary endpoint analyses.

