- For participants who consent to participate in the trial during the urgent healthcare visit for an acute COPD exacerbation, Visit 1b should be completed immediately after providing written informed consent and verifying eligibility.

b The Screening Period after Screening Visit 1b is up to 48 hours. Any procedures completed as part of the assessment and treatment of the COPD exacerbation may be used for Screening (eg, hematology, clinical chemistry, urinalysis, β -hCG if applicable, spirometry, chest X-ray or CT, ECG). Note that the maximum combined number of chest X-rays and/or CT scans must not exceed 2 for screening.

c Randomization/Baseline Visit is defined as Day 0 (Visit 2). Screening Visit 1b and Day 0 (Visit 2) may be the same day or up to 48 hours apart. If Visit 1b and Day 0 (Visit 2) are the same day, then FeNO and post-BD spirometry do not need to be repeated. For ECG, complete physical exam, and height/weight the Visit 1b assessment will serve as Baseline. All assessments at Visit 2 (Day 0) are to be conducted pre-IP dose administration with the exception of the assessment of SC injection sites and post-IP administration vital sign measurements.

d Visit 3 and Visit 4 are for participants who are hospitalized for current acute COPD exacerbation. Hospitalized participants discharged from the hospital prior to Visit 3 or Visit 4, or participants that were not hospitalized, should return to the trial site or have a home health care visit for spirometry assessments at Visit 3 and Visit 4 when feasible.

e At Visit 7, participants will be contacted by telephone.

f Medical history includes COPD history, COPD exacerbation history, past and current medical conditions (including cardiovascular and cerebrovascular medical history, surgical history), and substance usage.

g Participants will be trained on home use of the e-diary at Visit 2 and throughout the trial on an as needed basis. Participants will complete the assessment of EXACT-PRO every evening, and Dyspnea NRS and usage of short-acting rescue medications via e-diary twice daily at home.

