- t If the participant's condition allows, post-BD FEV₁ will be conducted approximately 15 to 30 minutes after the participant administers 4 inhalations of albuterol (salbutamol) via MDI (ie, total of 400 mcg) using a spacer device. It is anticipated that participants who are randomized into the trial will receive albuterol as part of the routine treatment of COPD exacerbation during Visit 2. In this case, spirometry should be scheduled to coincide with this treatment to allow post-BD recordings to be measured.
 - u For hospitalized participants, post-BD spirometry should also be performed at Visit 3 and Visit 4 provided the participant's condition allows. Hospitalized participants discharged from the hospital prior to Visit 3 and/or Visit 4, and participants who were not hospitalized, should be encouraged to return to the trial site or have a home health care visit for spirometry assessments at Visit 3 and Visit 4.
 - v Participants should complete the EXACT-PRO as follows: At Visit 2, complete the assessment while at the site as the first assessment before IP administration and prior to completing other trial assessments/procedures (may be completed in the morning or the afternoon); thereafter, it will be completed daily in the evening (typically at bedtime).
 - w Participants should complete CAT prior to the SGRQ and other trial assessments/procedures. CAT will be captured electronically using a handheld device at the site visit or paper questionnaires at the telephone call visit (Visit 7). Electronic upload of a participant completed paper questionnaire is permitted when use of the electronic questionnaire is not possible.
 - x SGRQ will be captured electronically using a handheld device at the site. Participants should complete the SGRQ after the CAT and prior to other trial assessments/ procedures.

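### Baseline FEV₁ has no fallback to an earlier-day, pre-dose Visit 1b value, so participants without a Visit 2 test leave a secondary analysis said to use the FAS

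*Protocol*

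**What the plan says.** Section 10.3 fixes the definition: baseline FEV₁ "is defined as the post-BD FEV₁ performed at Visit 2 before IP administration". One accommodation follows: "If Visit 1b and Day 0 (Visit 2) are the same day, then post-BD spirometry does not need to be repeated". The same section makes the test conditional: "if the participant's condition allows, post-BD FEV₁ will be conducted approximately 15 to 30 minutes after" inhaled albuterol. The post-BD footnote to the Schedule of Assessments (Appendix A) repeats that condition.

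On timing, Appendix A says: "Screening Visit 1b and Day 0 (Visit 2) may be the same day or up to 48 hours apart". It then lists what may be taken from Visit 1b: "For ECG, complete physical exam, and height/weight the Visit 1b assessment will serve as Baseline". Spirometry is not in that list.

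Table 2 makes absolute change from baseline in post-BD FEV₁ at Day 3, Week 1 and Week 4 a secondary endpoint. Section 13.4.6 analyses it with an MMRM that "will include covariates for the stratification factors and the respective baseline value of the continuous outcome", and names the FAS, which Section 13.3 defines as everyone randomized and dosed.

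Two further places show that a pre-dose Visit 1b value is foreseen. Section 8.2.2.3 expects albuterol to be given at both Visit 1b and Visit 2 and asks for spirometry to be timed with it so that post-BD readings are obtained. Footnote b of Appendix A counts spirometry among the care procedures that may be used for Screening.

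**The concern.** Visit 2 takes place during the index exacerbation, when a forced manoeuvre is hardest to perform, so some Visit 2 tests can be expected to be missed. Without that value a participant has neither a change score at any visit nor the model covariate, however complete the later spirometry. The model as written cannot then analyse the set it names.

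This is a rule the protocol states, not a detail it leaves open. The protocol is also uneven: Table 2 lets exploratory pre-BD FEV₁, and the other exploratory lung-function measures, be referred to the earliest measurement on hand, while the higher-ranked post-BD FEV₁ endpoint has no such provision. At stake are usable pre-dose data, some precision, and how closely the analysed participants match the FAS.

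**Working it through.** **The plan's own figure.** Section 13.2 randomizes 160 and allows 5% dropout: 160 × 0.95 = 152, or 76 per arm. For 45% against 22.5%, two-sided 5%, pooled variance and no continuity correction, power at 76 per arm is 84.2%, which agrees with the stated 80% or more. That figure concerns the primary endpoint, which does not use FEV₁. No SD, effect size or missing-baseline rate is given for FEV₁. I use 152 as a convenient base; the SE ratios below do not depend on it.

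**Who has a baseline under Section 10.3.**
- Visits on the same day, test done: baseline exists.
- Visits on different days, Visit 2 test done: baseline exists.
- Visits on different days, no Visit 2 test, Visit 1b post-BD value exists: no baseline, although a pre-dose value is on file. Only this group is helped by a fallback.
- No pre-dose value at all: no baseline under either rule.

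**Size.** Let m be the share without a Visit 2 value and f the share of those with a usable Visit 1b value. Both are assumptions.
- Analysed under the present rule: 152(1 − m). SE multiplier relative to a baseline for everyone: 1/√(1 − m).
- Analysed with the fallback: 152(1 − m(1 − f)). SE multiplier: 1/√(1 − m(1 − f)).

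With f = 0.5:

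| m | Present rule | SE × | With fallback | SE × | Restored |
|---|---|---|---|---|---|
| 5% | 144.4 → 144 | 1.026 | 148.2 → 148 | 1.013 | 4 |
| 10% | 136.8 → 137 | 1.054 | 144.4 → 144 | 1.026 | 7 (7.6 before rounding) |
| 20% | 121.6 → 122 | 1.118 | 136.8 → 137 | 1.054 | 15 |

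With f = 0.25 the analysed numbers are 146, 141 and 129 (2, 4 and 7 restored). With f = 0.75 they are 150, 148 and 144 (6, 11 and 22 restored).

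**In power terms.** For a comparison with 80% power at 152, power is Φ[(1.960 + 0.842)√(share analysed) − 1.960]. Under the present rule this gives 78.0%, 75.7% and 70.7%. With the fallback at f = 0.5 it gives 79.0%, 78.0% and 75.7%.

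**Bias.** A simulation of a single-visit ANCOVA (3000 runs, 160 participants) used assumed values: baseline mean 1.20 L, SD 0.40 L, residual SD 0.25 L, true effect 0.10 L, and a missing baseline more likely when FEV₁ is low.
- About 11% lacked baseline, and the mean baseline of those analysed rose from 1.20 to 1.25 L.
- With a constant effect, the estimate was 0.100 L with everyone and 0.100 L after the loss. Its SD rose from 0.0398 to 0.0423, a factor of 1.06, in line with 1/√(1 − 0.108) = 1.06.
- With an effect growing by 0.05 L per SD fall in baseline, the estimate moved from 0.100 to 0.094 L.

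**Constrained longitudinal model.** For participants with no pre-dose value at all, treating baseline as a response gives relative information of about 1 + [m/(1 − m)](1 − ρ²). This ranges from 1.019 (m = 5%, ρ = 0.8) to 1.188 (m = 20%, ρ = 0.5).

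**The case against.** The strongest reply is that a rule for a missing baseline is a data convention. Section 13 leaves those to the SAP, Section 13.6 defers further missing-data detail there, and Section 13.4.1 lets the SAP describe changes from the planned analysis. The SAP may already deal with this. That stands in part: the remedy could be placed in the SAP. But Section 10.3 states a definition that excludes the earlier-day value, so an SAP fallback would be a departure from the protocol to be declared and justified.

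The affected group may also be small. The same-day rule already covers part of the population. Exclusion 19 removes some of the most severe cases, participants needing acute CPAP cannot be enrolled (Section 8.2.2.2), and sites are told to time spirometry with albuterol. Someone too ill to blow at Visit 2 may have been too ill at Visit 1b. All of this stands and limits the gain. In addition, the efficacy rows of Table 5 were not in the text available to me, so post-BD spirometry at Visit 1b is inferred from the provisions cited above.

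Finally, using the value from the dosing visit is defensible, since an older value may come from a different point in recovery on corticosteroids. That is a genuine trade-off, but a value at most 48 hours old is preferable to discarding the participant.

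Four stronger readings may tempt a reader, and the documents support none of them.
- That baseline can come only from Visit 2: the same-day rule says otherwise.
- That the analysis drops the sickest participants: this is plausible from the condition on testing, but no exclusion rule or missing rate is stated.
- That the full SE increases in the present-rule column are what the fallback would save: they compare with a baseline for everyone, and the fallback recovers only part.
- That the arm comparison is biased: baseline is measured before dosing and under blind.

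**Conclusion.** The point holds for a defined group: participants whose Visit 1b falls on an earlier day, who have no Visit 2 post-BD test, and who have a usable Visit 1b value. Following Section 10.3 discards that value and removes them from an analysis described as using the FAS.

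The consequence is modest: lost precision and a somewhat narrower population on one secondary endpoint. Restoring about 4, 7 or 15 of 152 rests on two assumptions the protocol does not inform, namely 5%, 10% or 20% missing at Visit 2 and half of those having a Visit 1b value. The treatment estimate shifts only if the effect also varies with baseline FEV₁, and in the assumed example the shift was 0.006 L. It would go too far to say that the result no longer applies to the randomized population. The primary endpoint and the sample size are unaffected.

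**What to change.** In Section 10.3, define baseline FEV₁ as the last acceptable post-BD value before IP administration: Visit 2, otherwise Visit 1b. Add a sentence to Section 13.4.6, or to the SAP, saying how participants with no pre-dose value are handled. Settle both before unblinding, because a fallback chosen afterwards would be open to challenge.

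No new data are needed. The downside is that some baselines will be up to 48 hours older; reporting how many came from Visit 1b would make this visible.

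The MMRM is a standard choice and need not be replaced. A constrained longitudinal model, with baseline in the response vector and equal arm means, could be added as a sensitivity analysis so that FAS participants with any post-BD FEV₁ contribute.
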